6. PARTICIPANT IDENTIFICATION

6.1. Study Participants

This study will recruit trauma patients, aged 60 years or older, undergoing hemiarthroplasty following hip fracture.

6.2. Inclusion Criteria

The participant must meet ALL of the following criteria:

- 1) Provision of informed consent OR consultee declaration
- 2) Aged 60 years or over
- 3) Presenting with fracture of the hip
- 4) Scheduled to undergo hemiarthroplasty

6.3. Exclusion Criteria

The participant may not enter the study if ANY of the following apply:

- 1) Previous surgery or infection of the affected hip
- 2) Hip fractures related to polytrauma
- 3) Patients managed without hemiarthroplasty
- 4) Receiving an investigational medicinal product related to infection

7. STUDY PROCEDURES

7.1. Recruitment

The pilot study will recruit at three centres (Brighton, Oxford and Northumbria) in the first instance, each of which will aim to recruit a minimum of 100 participants in 12 months. Provision will be made to include up Additional File 2 RIIiO Pilot Protocol v4.0.docx CONFIDENTIAL

to six further centres after six months. This will provide a mechanism to most accurately determine the total number of sites required for the definitive trial.

Research networks -

Recruitment to the definitive trial will take place through specialist centres drawn from the following networks:

- 1) The World Hip Trauma Evaluation (WHiTE) cohort, which is a comprehensive cohort study of patients with hip fracture treated at 16 specialist units in England. Since May 2015, WHiTE has recruited in excess of 300 patients per month. All patients are treated under a single comprehensive treatment pathway based upon the NICE Hip Fracture Guidelines and have core outcome measurements collected within the framework of the UK National Hip Fracture Database.
- 2) The United Kingdom Clinical Infection Research Group (UKCIRG) is a network of NHS infection specialists with specific expertise in the prevention, diagnosis and treatment of SSI. It recruits at 43 centres across the UK. UKCIRG studies currently include a 27-centre intervention trial looking at the management of orthopaedic infections (OVIVA), and a 30-centre intervention trial investigating adjunctive therapy in Staphylococcus aureus bacteraemia (ARREST).

Trainee networks -

Recruitment to both the pilot study and to the definitive trial will promote trainee network engagement in clinical research as part of improving research accessibility with NHS practice, and will provide a mechanism for optimising screening and recruitment at individual sites.

- 1) The Trauma Audit and Research Network (TARN)
- 2) The Research and Audit Federation for Trainees (RAFT) network in anaesthetics
- 3) The National Infection Trainee Collaborative for Audit and Research (NITCAR)

7.2. Screening and Eligibility Assessment

Potential participants will be identified during their routine care pathway from admission records, theatre lists and at daily trauma meetings at each recruiting site. Determination of eligibility for this study will be based on a review of the case notes and a clinical assessment in relation to the inclusion and exclusion criteria defined above. There are no other specific screening investigations and no additional laboratory or diagnostic tests will be required.

7.3. Informed Consent

Patients with a hip fracture are a clinical priority for urgent operative care and will usually undergo surgery on the next available operating list. Such patients have a high incidence of comorbidities, will inevitably have suffered trauma and are likely to either be in pain or to have received opiate analgesia. It is therefore understandable that patients find their initial treatment in hospital frightening, confusing or disorientating. In this situation, the focus necessarily lies on obtaining consent for surgery (where possible) and on informing the patient and next of kin about the immediate clinical care plan. It is often either inappropriate or not possible to ask potential participants to review trial documentation, weigh up the information and communicate an informed decision as to whether they would wish to participate.

Conducting research in an emergency setting is regulated by the Mental Capacity Act 2005. Given the number of factors influencing capacity or the ability to communicate an opinion, we will act in accordance with section 32, subsection 9b of the Mental Capacity Act. Those patients who are listed for surgery on the next available operating list will not be approached for consent prior to their surgery but we will approach an appropriate consultee. They will be provided with the study information and be given the opportunity to ask questions and discuss the study, after which their verbal agreement will be recorded. Where possible and appropriate, a personal consultee will be approached. Where necessary, a nominated consultee will be identified to advise the research team. The nominated consultee will be a clinician responsible for the

patient during their admission unless they are also a member of the research team, in which case an independent clinician will be asked to provide an opinion.

At the earliest appropriate opportunity after recovery from surgery, a member of the research team will approach randomised participants to provide them with study information and to seek written personal consent to continue in the study. They will be given as much time as they wish to discuss the study, to ask questions and talk to their family and carers. For those who have persisting lack of capacity, written agreement from a personal consultee will be sought. Participants (or their representatives) who do not wish to be contacted or who do not wish to complete questionnaires will be asked for consent to allow the research team to access and use routinely captured NHS data; these may include data recorded by their GP, the National Hip Fracture database and the Surgical Site Surveillance database. Alternatively, the participant (or their representative) can decline participation completely. The Information Sheet, consent form and consultee declaration state clearly that participants or consultees can withdraw their consent or advice at any time without giving a reason.

Signed consent forms will be stored in the investigator site file. A copy will be given to the participant (or their representative) and a copy will be placed in the participant's medical notes.

On occasion, patients may be able to provide consent before their operation, for example those whose surgery is delayed for clinical reasons. These patients will be approached prior to surgery for consent to participate in the study. If, despite delayed surgery, a patient lacks capacity the research team will approach a consultee.

Best efforts will be made to involve participants who, temporarily or permanently, lack capacity to make an informed decision. The research team will make a judgement as to the amount and complexity of the information that the patient is able to understand and retain on an individual basis. Appropriate information will be communicated to the participant and updated as their understanding changes. At all times the study team will act in accordance with the participant's best interests.

Any new information that arises during the study that may affect participants' willingness to take part will be reviewed by the TSC; if necessary this will be communicated to all participants and a revised consent form prepared.

Responsibility for documenting informed consent or agreement will lie with the investigator or persons designated by the investigator who conducted the consent discussion. The person who receives consent will be suitably qualified, experienced and authorised to do so by the Principal Investigator. Designated responsibility will be recorded in the site delegation log.

7.4. Randomisation and limitation of bias

Prior to surgery, participants will be randomised 1:1 in randomly permuted blocks through an established software package to either Forced Air Warming or direct contact Resistive Fabric Warming. No stratification factors will be employed. In case of software failure, randomisation envelopes will be prepared in advance under the supervision of a qualified statistician and held by the local study team for immediate use in the emergency setting.

This will be an open label trial. Although participants will not be directly informed of their randomised allocation, they may become aware of this either immediately before or upon recovery from anaesthesia. Similarly, it is not possible to blind the direct medical care team or the local study team as to which warming technology is utilised during surgery. Any consequent risk of bias will be limited by the use of a blinded end point committee for the assessment of relevant potential endpoints. For all potential deep SSIs, the end point committee will be provided with a summary of the participant's medical records relevant to the clinical episode, (including presentation, operative findings, laboratory results, radiology reports and treatment) redacted for personal identifiers and any information relating to their randomisation or intraoperative thermoregulation. At the time of randomisation, the participant's initials, NHS number and a computer-generated study number will be recorded on an enrolment log. Justification for use of NHS numbers comes from previous multicentre studies in which the randomisation software requires all

participants to have a primary identifier of the same alphanumeric structure and with no opportunity for duplicates.

7.5. Baseline and Perioperative Assessments

Data for baseline assessments will be captured from routine clinical care records. The local study team will record the following in the CRF:

- 1) Age
- 2) Gender
- 3) Weight/Height (to derive Body mass index)
- 4) American Society of Anaesthesiologists (ASA) physical status classification
- 5) Anatomical side affected
- 6) Date of admission
- 7) Date of surgery
- 8) Randomisation arm (FAW or RFW)
- 9) Adherence to randomised strategy
- 10) Duration of surgery
- 11) Use of UCV in theatre
- 12) Surgical procedure
- 13) Antimicrobial prophylaxis
- 14) Immuno-suppressants
- 15) Co-Morbidities
- 16) Continuous temperature monitoring (3M SpotOn Zero Flux Thermometry)
- 17) Baseline EQ-5D-5L measures

7.6. Subsequent Assessments

The participant will be contacted for follow-up at the following time points after surgery:

- 1) 30 (+/- 7) days
- 2) 90 (+/- 14) days

Follow-up assessments will be undertaken by a member of the local study team through a) medical records and b) direct contact, usually by telephone, with the participant or their consultee. The participant will not be asked to attend any research specific clinic visits and they will not be visited at home by the study team. If it is not possible to make contact with the participant, the local study team will gather follow-up data from the patient's GP and from routinely collected surveillance data. At each time point, we will ask questions about the participant's wellbeing, surgical scar and any treatment or concerns around possible infection at the operative site. Where necessary, further clinical review will be requested.

The study will use the participant follow-up telephone questionnaire in Appendix A as a research tool when gathering patient reported outcome measures for quality of life (PROMS) and any relevant concerns they have. Instructions to the participant will be dictated from the EQ-5D-5L telephone questionnaire in Appendix B. If a patient lacks capacity, the EQ-5D-5L Proxy version 1 will be used (Appendix C).

Deep SSI will be defined by the following criteria:

- a. Infection arising within 90 days of the index surgery (where day 1 is the procedure date) AND
- b. Involves deep tissues related to the incision (e.g. fascial and muscle layers, joint space or periprosthetic region)

AND

- c. At least one of the following
 - i. Purulent drainage from the deep incision or periprosthetic drain.
 - ii. A deep incision that spontaneously dehisces, or is deliberately opened or aspirated or biopsied by a surgeon, physician or other designee and an organism is identified by a culture or non-culture based microbiologic testing method which is performed for purposes of clinical diagnosis or treatment (e.g., not Active Surveillance Culture/Testing) or culture or non-culture based microbiologic testing method is not performed
 - An abscess or other evidence of infection involving the deep incision or periprosthetic region that is detected on gross anatomical, histopathological exam or imaging test

Superficial SSI will be defined by the following criteria:

- a. Infection arising within 30 days of the index surgery (where day 1 is the procedure date) AND
- b. Involves only skin or subcutaneous tissue related to the incision AND
- c. At least one of the following
 - i. Purulent drainage from the superficial incision
 - ii. Organisms identified from an aseptically-obtained specimen from the superficial incision or subcutaneous tissue by a culture or non-culture based microbiologic testing method which is performed for purposes of clinical diagnosis or treatment (e.g., not Active Surveillance Culture/Testing (ASC/AST).
 - Superficial incision that is deliberately opened by a surgeon, physician or other designee and culture or non-culture based testing is not performed AND
 the patient has at least one of the following signs or symptoms: pain or tenderness, localized swelling, erythema, heat
 - iv. Diagnosis of a superficial incisional SSI by a surgeon or physician.

The above definitions are adapted from the CDC surgical site infection criteria published January 2016. If required for clarification or consensus, investigators and the EPC will be referred back to the source document.

Serious adverse events (SAEs), including death (i.e. all-cause mortality), will be recorded.

Discontinuation/Withdrawal of Participants from Study

Once a participant has been randomised, they will ordinarily be included in the intention to treat (ITT) analysis. However, the Principal Investigator at each site will withdraw any randomised participant from the study if they do not subsequently undergo surgery. Each participant or their consultee has the right to withdraw from the study at any time with no obligation to give a reason for withdrawing. The participant will be asked whether or not they will allow passive follow up using routinely available NHS data. All data collected up until the point of withdrawal of consent will be included in the final analysis unless requested otherwise by the participant.

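### Deep SSI item c(ii), the only one that accepts an identified organism, names just the deep incision, so infection proven only by closed joint or periprosthetic sampling fails the printed endpoint

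*Protocol*

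**What the plan says.** Protocol section 7.6 defines deep SSI by three limbs, all of which must be met: (a) onset within 90 days, (b) the tissue involved, and (c) at least one of three items of evidence.

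- Limb (b): "Involves deep tissues related to the incision (e.g. fascial and muscle layers, joint space or periprosthetic region".
- Item c(i): "Purulent drainage from the deep incision or periprosthetic drain".
- Item c(ii): "A deep incision that spontaneously dehisces, or is deliberately opened or aspirated or biopsied by a surgeon, physician or other designee", combined with either a positive result ("an organism is identified by a culture or non-culture based microbiologic testing method") or no test having been done.
- Third item of (c): "An abscess or other evidence of infection involving the deep incision or periprosthetic region", which must be "detected on gross anatomical, histopathological exam or imaging test".

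The superficial definition in the same section has its own microbiology item: "Organisms identified from an aseptically-obtained specimen from the superficial incision or subcutaneous tissue".

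Section 7.6 describes both definitions as adapted from the CDC criteria and adds: "If required for clarification or consensus, investigators and the EPC will be referred back to the source document". Section 5 describes the primary endpoint as CDC-defined and has a blinded committee decide each potential event by consensus or, failing that, majority vote.

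**The concern.** The tissue limb and the evidence limb do not match. Limb (b) admits infection of the joint and around the implant. In limb (c), the one item that accepts a positive microbiology result is tied to the incision. A patient whose joint fluid, drawn by needle under a healed wound, grows an organism can satisfy (a) and (b) and still fail (c).

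The definition serves the primary endpoint. Under section 10.1 the pilot's deep SSI rate informs the design of the main study, and under section 3 the pilot data carry into the final analysis. A true implant infection left out by wording would lower that rate. If committee members differ over how far c(ii) reaches, the same case could be decided either way.

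**Working it through.** **Step 1. Compare the sites and evidence named in each part of the deep SSI definition (section 7.6).**

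| Part | Deep incision | Joint or periprosthetic site | Evidence accepted |
|---|---|---|---|
| Limb (b) | tissues related to it | both named | not applicable |
| c(i) | named | periprosthetic drain | pus |
| c(ii) | named | none | organism identified, or no test done |
| Third item of (c) | named | periprosthetic region | gross anatomy, histology, imaging |

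Two of the three items list a periprosthetic site alongside the deep incision. The drafting therefore treats them as different things, and it is unsafe to read the joint into c(ii). The third item names the region but does not list culture among its modes of detection. The superficial microbiology item covers both tissue levels of its own limb (b).

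**Step 2. Apply the rule to cases that meet (a) and (b).**

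- *Incision reopened, joint fluid or periprosthetic tissue grows an organism.* This meets c(ii). The item requires an opened incision and an identified organism and does not say where the specimen must come from.
- *Incision not reopened, but pus from the incision or a drain.* This meets c(i).
- *Incision not reopened, but a gross, histological or imaging finding.* This meets the third item.
- *Closed joint aspirate or percutaneous periprosthetic biopsy grows an organism, with none of the above.* This meets no item of (c).

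Only the last case is lost.

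**Step 3. Reproduce the sample size in section 3.** Inputs: 2.5% risk, 1% absolute reduction (so 1.5%), 90% power and 5% significance (section 3); 1:1 allocation (section 7.4). Sidedness is not stated, so two-sided is assumed.

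Uncorrected size per arm, with d = 0.010 and mean risk 0.020:

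n = [1.960·√(2·0.020·0.980) + 1.2816·√(0.025·0.975 + 0.015·0.985)]² / d² = (0.3881 + 0.2536)² / 0.0001 ≈ 4117

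With continuity correction:

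N = (n/4)·[1 + √(1 + 4/(n·d))]² ≈ 4314.5, rounded up to 4315 per arm, or 8630 in total. This matches the protocol. Without the correction the total is 8234.

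**Step 4. Illustrate the effect of a missed share s.** The documents give no value for s. Assume it is the same in both arms, so the risks become 2.5%·(1 − s) and 1.5%·(1 − s) and the risk ratio stays at 0.6. Hold N at 4315 per arm and undo the continuity correction with n = (N − 1/d)²/N. Then:

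Power = Φ{ [d·√n − 1.960·√(2·p̄·(1 − p̄))] / √[p₁(1 − p₁) + p₂(1 − p₂)] }

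| s (assumed) | Risks | Power at 8630 |
|---|---|---|
| 0% | 2.500% v 1.500% | 90.0% |
| 1% | 2.475% v 1.485% | 89.7% |
| 3% | 2.425% v 1.455% | 89.1% |
| 5% | 2.375% v 1.425% | 88.4% |
| 10% | 2.250% v 1.350% | 86.5% |

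**Step 5. Put it on the pilot's scale.** Three sites at 100 participants each (section 7.1) and a 2.5% risk give 300 × 0.025 = 7.5 expected events. A share of 10% would remove 0.75 of an event and 1% would remove 0.075. The Poisson standard deviation is √7.5 ≈ 2.7.

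**The case against.** The strongest reply is that the lost case is rare. Section 3 states that deep infections nearly always lead to another operation. An operation through the wound brings a culture-positive case within c(ii), and operative findings can also satisfy the third item. Section 7.4 gives the committee operative, laboratory and radiology information, so these routes can be judged. This stands, and it limits the size of the point.

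A second reply is that experts in bone and joint infection would read c(ii) together with limb (b), which treats the joint as deep tissue related to the incision, and that c(ii) itself mentions aspiration. The reading is possible, but it sits badly with the two neighbouring items that list periprosthetic sites separately.

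A third reply is that section 5 ties the endpoint to the CDC and section 7.6 allows referral to the source. This softens the gap without closing it. Referral happens only when clarification or consensus is needed, and a committee that agrees the printed text is not met needs neither. The protocol also does not say whether the adapted text or the source prevails. The source is not at hand, so what it says on this case is not assumed here.

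A reader might also infer that c(ii) accepts only specimens taken from the incision itself, so that any culture of periprosthetic tissue is excluded. The text does not say so: c(ii) names no specimen source, and reopening the incision with a positive culture is enough.

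**Conclusion.** Wrong as written, in a narrow respect. The printed rule rejects an infection that meets limbs (a) and (b) and is proven only by an organism from closed joint or periprosthetic sampling. It is counted only if the committee reads c(ii) broadly or chooses to consult the source.

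The under-count is probably small. Its size, and any loss of power, cannot be computed from the documents. The power figures are illustrations that rest on three assumptions: the missed share itself, the same share in both arms, and a 2.5% design rate measured under a definition that does count these cases. The protocol does not support or contradict any of the three. A share of 1% to 3% would cost less than one percentage point.

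A reader might infer that the full trial will miss its 90% power. The documents do not support that. They give no missed share, section 3 points to a low one, and section 10.1 allows the main design to change in the light of the pilot. Nothing here suggests bias between the arms.

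**What to change.** Bring the site wording of c(ii) into line with limb (b), for example by adding: *or an organism is identified, by testing performed for clinical diagnosis or treatment, from aseptically obtained fluid or tissue from the joint space or periprosthetic region*. Use the same wording in the endpoint committee's instructions. If any referral was rejected solely because no item of (c) was met, have the blinded committee re-read it; the protocol does not show whether any exists.

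The cost is one sentence in two documents and at most a few re-readings. The downside is that a single contaminated aspirate could meet the added item, which the blinded committee is placed to judge.

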5. TRIAL DESIGN

The overall trial design, depicted in the flowchart below, is a parallel group, open label study randomising to RFW or FAW in permuted blocks in adults aged 60 years or over who are undergoing hemiarthroplasty following hip fracture. The trial has been designed with input from cross-specialty hospital consultants, patient representatives, a statistician and a clinical trials unit. This pilot study will recruit for a minimum of one year at each site, allowing for refinements to design, site selection and, if necessary, the data management strategy in preparation for a large multi-centre trial.

Participants will be expected to remain in the trial for approximately three months. They will not need to attend any research specific clinics or undergo any study specific clinical investigations. The primary endpoint is numbers recruited and observed event rate for definitive deep surgical site infection (SSI) within 90 days as defined by the Centre for Disease Control (CDC). All potential primary endpoints will be confirmed by a blinded endpoint committee. The secondary endpoints include serious adverse events including death, superficial SSI, IPH, length of hospital stay, patient reported outcome measures (EQ-5D-5L) and resource utilisation. Data for all assessments will be captured either from routine clinical care records or by telephone contact with participants or their GP practice at baseline, 30 (+/- 7) days and 90 (+/- 14) days. Patients will be flagged and mortality checks performed at each time point before the local study team makes contact for follow-up. Where a potential deep SSI is identified, a summary of the clinical care record, redacted for all personal identifiable information and any indication of randomisation arm, will be forwarded to the independent blinded endpoint committee.

CONFIDENTIAL Page 11 of 34

Endpoint Committee

The endpoint committee, which will remain blind to allocation, will comprise clinicians with expertise in the diagnosis and management of bone and joint infection. The committee will have a chair and two other members. If any endpoint committee member stands down during the course of the trial, they will be replaced by someone with similar background and qualifications.

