Any post-randomisation re-admission, clinic attendance or return to theatre with signs and symptoms at the site of surgery (i.e. possible deep surgical site infections) will be considered a potential primary endpoint. A summary of the relevant medical record, redacted for personal identifiers and information relating to randomisation, will be forwarded to the blinded endpoint committee who will determine if an endpoint has been met. Determination of an endpoint will be by consensus following discussion or by a majority vote called by the chair if consensus cannot be reached.

Secondary endpoints, including SAEs and data for resource utilisation, will be determined directly by the local investigators.

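### Deep SSI criterion c(ii) can be met by an opened, unsampled deep incision with no sign or symptom of infection, whereas the matching superficial branch requires one

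*Protocol*

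**What the plan says.** Section 7.6 of the Protocol defines deep SSI by three limbs joined by AND.

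- Limb (a): "Infection arising within 90 days of the index surgery (where day 1 is the procedure date").
- Limb (b): "Involves deep tissues related to the incision (e.g. fascial and muscle layers, joint space or periprosthetic region").
- Limb (c): at least one of three items. The second, c(ii), starts from "A deep incision that spontaneously dehisces, or is deliberately opened or aspirated or biopsied by a surgeon, physician or other designee". It is completed either by an organism being identified, "or culture or non-culture based microbiologic testing method is not performed".

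Superficial SSI, in the same section, has a parallel item, the third under its limb (c): an incision deliberately opened and not tested. There the protocol adds, after a further AND, that "the patient has at least one of the following signs or symptoms: pain or tenderness, localized swelling, erythema, heat".

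Three other provisions bear on the point.

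- Section 5 (Endpoint Committee) sets the referral rule, which applies in the same way to readmissions and outpatient visits: "return to theatre with signs and symptoms at the site of surgery (i.e. possible deep surgical site infections) will be considered a potential primary endpoint".
- Section 5 also states: "All potential primary endpoints will be confirmed by a blinded endpoint committee".
- After the two definitions, section 7.6 says they are adapted from CDC criteria and adds: "If required for clarification or consensus, investigators and the EPC will be referred back to the source document".

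**The concern.** The no-test branch of c(ii) is reached through an event (dehiscence or opening) plus the absence of a test. Neither shows infection. Limb (b) is anatomical, and the word infection in limb (a) has no test of its own, so limb (c) has to carry the evidence, and on this branch it carries none. A wound that dehisces or is re-opened for a mechanical reason or a haematoma, with no sample sent, satisfies c(ii) as written.

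Deep SSI within 90 days is part of the pilot's primary endpoint (sections 1 and 5) and is the main-trial primary outcome (section 4). Section 10.1 uses the pilot rate to inform the main design, and section 3 carries pilot data into the final analysis. Non-infective events counted in both arms would inflate the rate and dilute the contrast. The branch also turns on whether a sample was sent. The direct care team, which section 7.4 says cannot be blinded, is in a position to influence that, and no later review can recover a test that was never done.

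**Working it through.** **1. The two no-test branches side by side (section 7.6)**

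| | Deep, c(ii) | Superficial, third item of (c) |
|---|---|---|
| Opening clause, limb (a) | infection arising, 90 days | infection arising, 30 days |
| Event | dehiscence, opening, aspiration or biopsy | deliberate opening |
| Test | none done | none done |
| Sign or symptom | not required | at least one required |

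Both definitions begin with an infection clause. In the superficial definition that clause was not treated as enough for an untested wound. No reason is given for treating it as enough in the deep one.

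**2. The plan's own figure**

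Inputs from section 3: 2.5% deep SSI, absolute reduction 1% (so 1.5%), 90% power, 5% significance (taken as two-sided), about 8630 participants. Allocation is 1:1 (section 7.4).

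Uncorrected n per arm = [1.960·√(2·p̄·(1−p̄)) + 1.2816·√(p1(1−p1) + p2(1−p2))]² / d²

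With p̄ = 0.02 and d = 0.01: [1.960·√0.0392 + 1.2816·√0.03915]² / 0.0001 = 4117 per arm, 8234 in total.

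Continuity-corrected n = (n/4)·[1 + √(1 + 4/(n·d))]² = 4315 per arm, 8630 in total. This reproduces the stated figure exactly, so the continuity-corrected basis is used below.

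**3. Illustration of size**

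Let f be the share of non-infected patients in each arm counted through the no-test branch. The documents give no value; 0.25% to 1% is an assumption. The observed rate becomes p + f(1−p).

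Power at 4315 per arm: put n′ = 4315·[1 − 1/(4315·d)]², then z = [d·√n′ − 1.960·√(2·p̄·(1−p̄))] / √(p1(1−p1) + p2(1−p2)).

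Worked for f = 1%:
- Rates are 0.025 + 0.01×0.975 = 0.03475 and 0.015 + 0.01×0.985 = 0.02485, so d = 0.0099 and p̄ = 0.0298.
- n′ = 4115.
- z = (0.6351 − 0.4713)/0.2404 = 0.681, so power is 75.2%.

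| f (assumed) | Observed rates | Relative risk | Non-infective share of counted events | Power at 8630 | Total N for 90% |
|---|---|---|---|---|---|
| 0 | 2.50% v 1.50% | 0.60 | 0 | 90.0% | 8630 |
| 0.25% | 2.74% v 1.75% | 0.64 | 11% | 86.3% | 9664 |
| 0.5% | 2.99% v 1.99% | 0.67 | 20% | 82.6% | 10702 |
| 1% | 3.48% v 2.49% | 0.72 | 33% | 75.2% | 12796 |

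The non-infective share is f×0.98 divided by the mean of the two observed rates; for f = 1% this is 0.0098/0.0298 = 33%.

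At pilot scale, three initial centres at the minimum of 100 each (section 7.1) give 300 participants. With a mean true rate of 2% that is 6 true events. The extra events would be 300×0.98×f, or 0.7 at f = 0.25% and 2.9 at f = 1%.

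**The case against.** The case on the other side is substantial.

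- **The definition is conjunctive.** A reader might infer that non-infective re-openings count as endpoints. The text does not say so: they can satisfy c(ii), but a re-opening known to be non-infective fails limb (a). This stands, and it confines the point to cases where the cause is in doubt.
- **Signs and symptoms are already needed for referral.** Section 5 requires them at the surgical site. But they are unspecified, and pain or swelling from a mechanical problem would pass. Equally, a list as general as the superficial one would not screen out every painful, swollen haematoma, which is why the added condition should speak of signs or symptoms of infection.
- **Blinded experts adjudicate.** The committee sees presentation, operative findings, laboratory results, radiology reports and treatment (section 7.4). This is the main protection and will catch obvious cases. Blinding limits bias by arm; it does not supply a criterion that the definition leaves out. Nothing in the documents shows that sampling would differ by arm, so differential bias should not be inferred.
- **The source criteria can be consulted.** Only where clarification or consensus calls for it. A committee that finds c(ii) clear has no prompt to look.
- **Is the primary endpoint looser than the secondary one?** Not as a general statement. Superficial c(iv) accepts a surgeon's or physician's diagnosis alone, and deep SSI has no such item. The contrast holds only between the two no-test branches.
- **Could an opened wound with a negative test count under c(ii)?** No. c(ii) needs an organism identified or no test performed, so a negative test already fails it.
- **The power figures.** They rest on an assumed f and concern a later trial whose analysis section 10.3 leaves pending the pilot's recommendations.

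**Conclusion.** The point holds in limited form. Section 7.6 states a rule for the no-test branch of deep SSI that is too loose, and the protocol's own superficial definition shows the missing condition. The safeguards narrow the consequence to unsampled dehiscences or re-openings of uncertain cause, whose classification depends on how the committee reads an undefined word. The effect is likely small and cannot be sized from the documents. The fall in power from 90% to about 86% to 75%, and the rise in the observed reference rate from 2.5% to about 2.7% to 3.5%, rest on an assumed 0.25% to 1% of non-infected patients being counted equally in both arms after adjudication. They show direction and sensitivity and are not a forecast. The stated 8630 is correct on its own inputs. The correction is worth making because the pilot rate feeds the main design and the pilot data enter its final analysis.

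**What to change.** In section 7.6, extend the no-test branch of deep c(ii) with a further AND condition: the patient has at least one sign or symptom of infection. Reconcile the list with the CDC criteria that the protocol cites. Give the endpoint committee the amended text as its working definition, and re-check any case already adjudicated on this branch.

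No sentence on negative tests is needed. The cost is one sentence in the protocol, the same text in the committee's instructions, and a short re-check. No stated sample size and no aspect of patient management changes.
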